## 7.5 Safety

Unless specified otherwise, safety analyses described in this section will be conducted for the Safety analysis set.

### 7.5.1 Treatment Exposure

Extent of exposure to both study treatments (CB-839 and nivolumab), including treatment duration, total dose received (mg for CB-839 and mg/m^2 for nivolumab), number of cycles, will be evaluated by summary statistics (N, mean, standard deviation, median, minimum and

maximum). Percent of patients and cycles with dose delays and reductions will be calculated.

Exposures will be summarized by cohort for CB-839 and nivolumab separately.

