**6.0 CORE PROTOCOL****6.1 Objectives**

Primary Objectives	Primary Endpoints
To evaluate the safety and tolerability of CB-839 in combination with nivolumab for patients with advanced/metastatic clear cell Renal Cell Carcinoma (ccRCC), melanoma (MEL), and Non-Small Cell Lung Cancer (NSCLC)	Evaluation of clinical tolerability of CB-839 in combination with nivolumab, including dose intensity of CB-839, adverse events, and laboratory data
To evaluate anti-tumor effect of CB-839 in combination with nivolumab for patients with advanced/metastatic ccRCC, MEL, and NSCLC as assessed by investigator	Overall response rate (ORR) and duration of response (DOR) per Investigator assessed Response Evaluation Criteria in Solid Tumors (RECIST) v1.1
To evaluate anti-tumor effect of CB-839 in combination with nivolumab for patients with advanced/metastatic MEL by Independent Radiology Committee (IRC)	Overall response rate (ORR) and duration of response (DOR) by Independent Radiology Committee (IRC)-assessed Response Evaluation Criteria in Solid Tumors (RECIST) v1.1
Secondary Objectives	Secondary Endpoints
To select the recommended Phase 2 dose (RP2D) of CB-839 in combination with nivolumab for patients with advanced/metastatic ccRCC, MEL, and NSCLC	Based on an evaluation of adverse events, pharmacokinetics, pharmacodynamics and evidence of clinical activity
To evaluate the progression-free survival (PFS) and overall survival (OS) of CB-839 in combination with nivolumab for patients with advanced/metastatic ccRCC, MEL, and NSCLC by standard RECIST criteria	Assessed by progression-free survival (PFS) per RECIST v1.1 and overall survival (OS)
To evaluate anti-tumor effect of CB-839 as monotherapy in patients with advanced/metastatic MEL	Assessed by ORR, DOR and PFS per RECIST v1.1
Determine pharmacokinetics (PK) of CB-839 in combination with nivolumab	Non-compartmental method of analysis will be used to analyze the plasma concentrations of CB-839
Exploratory Objectives	Exploratory Endpoints
To evaluate the pharmacodynamic effects of CB-839 alone and in combination with nivolumab in patients with advanced/metastatic ccRCC, MEL, and NSCLC	To include evaluation of changes in peripheral blood immunophenotyping, tumor immune infiltrate and plasma glutamine levels

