## 11.0 TEST ARTICLE/STUDY DRUG

### 11.1 Test Article Administration

#### CB-839

Test article (CB-839) will be administered orally using a capsule (200 mg per capsule) or tablet (200 mg per tablet) formulation. CB-839 will be administered only to patients who have signed and dated an Informed Consent Form. CB-839 will be administered on Days 1 through 28 of each 28-day cycle and should be taken orally using the number of capsules or tablets directed in the Pharmacy Manual. CB-839 dosing will not be adjusted for body weight or surface area.

The first CB-839 dose of the day will be administered immediately after breakfast. The evening/second dose should be taken with a meal approximately 12 hr ( $\pm$  2 hr) after the morning dose.

On PK days (Cycle 1 Days 1 and 15, Cycle 2 Day 1 and Cycle 3 Day 1) patients should be instructed NOT to take their morning dose of CB-839 at home. On PK days, patients will have all predose procedures performed, take their dose of CB-839 with food then receive nivolumab. The time of dosing will be recorded in the clinic. The evening dose will be self-administered by the patient after all postdose activities have been completed. On non-PK collection days, patients will administer CB-839 per their usual administration schedule.

Patients who vomit their CB-839 dose should be instructed NOT to make up that dose and to report the frequency of vomiting occurrences associated with study drug administration to the site. Patients who report  $\geq$  3 incidences of vomiting associated with study drug administration will have a blood sample drawn for an unscheduled PK analysis.

Nivolumab: Nivolumab will be administered at a flat dose of 240 mg IV infusion over 60 min on Days 1 and 15 of each 28-day cycle. Nivolumab (Opdivo®) is supplied by Calithera as a

10 mg/mL solution for infusion following dilution. Please refer to the [nivolumab package insert](#) for specific instructions on nivolumab administration.

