### 16.4.2 DLT-evaluable Populations in Dose Escalation

DLTs will be evaluated during dose escalation. Unless doses are missed in Cycle 1 due to DLT(s), a patient must receive at least 75% of the planned CB-839 doses (43 of 56 total doses) to be considered evaluable for DLT. If a patient received less than 43 doses of CB-839 in the first 28 days of treatment for reasons other than a DLT, the patient will be considered non-evaluable for DLT and replaced. Patients must receive both doses of nivolumab in Cycle 1 in order to be evaluable for DLT.

Patients who discontinue the study prior to receiving the requisite study treatment administrations for reasons that include, but are not limited to, clinical/radiographic progression, voluntary withdrawal, or complications that the Principal Investigator considers secondary to the patient's malignancy will not be considered evaluable for DLT and will be replaced.

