## 5 STUDY DESIGN

Protocol CX-839-004 is a Phase 1/2 open-label study of the combination of CB-839 with nivolumab in patients with advanced/metastatic ccRCC, MEL, and NSCLC, as well as CB-839 monotherapy in patients with advanced/metastatic MEL. Sequential dose escalation of CB-839 with full dose nivolumab (CB-Nivo) will take place in patients with advanced ccRCC, advanced/metastatic MEL, or metastatic NSCLC. Subsequently, multiple disease-specific single-arm cohorts will be enrolled in which CB-839 will be administered in combination with the full approved dose of nivolumab. CB-839 will be administered at the RP2D established in dose escalation. Patients in dose escalation must be eligible for one of the dose expansion cohorts. CB-839 monotherapy will be administered at the previously established monotherapy RP2D of 800 mg PO BID (twice daily).

Dose escalation will use a 3+3 design and will enroll cohorts of 3-5 patients with advanced ccRCC, advanced/ metastatic MEL, or metastatic NSCLC at escalating doses as outlined in Table 6.3-1 in the protocol amendment 2. Patients will receive escalating doses of CB-839 in combination with the FDA-approved anti-PD-1 agent nivolumab. Nivolumab will be administered at the FDA-approved dose of 240 mg every 2 weeks without adjustment for body weight.

Dose limiting toxicities (DLTs) observed in Cycle 1 (first 28 days of dosing) will be used to determine escalation to the next dose level. In general, patients who experience a DLT will not receive further treatment with the study drugs.

The Maximum Tolerated Dose (MTD) is defined as the highest dose level with no more than 1 DLT reported in 6 DLT-evaluable patients.

During dose escalation, patients must receive at least 75% of the planned CB-839 administrations and both doses of nivolumab in the first 28-day treatment cycle to be considered evaluable for DLT, unless the patient has a DLT or has the study drug held for an adverse event (AE) that may herald a DLT.

The starting dose of CB-839 will be 600 mg BID. The first dose of CB-839 will be administered in the morning with breakfast. The second dose will be administered in the evening with a meal approximately 12 hr ( $\pm$  2 hr) after the morning dose.

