### 5.2.2 *Safety Endpoints*

The safety endpoints are:

- Type, incidence, seriousness, nature, severity, and drug-relatedness of adverse events graded according to the National Cancer Institute Common Terminology Criteria for Adverse Events, Version 4.0 (NCI CTCAE v4.0)
- Changes in vital signs, physical findings, and clinical laboratory test results following study treatment administration

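### The SAP reports flat-dosed nivolumab in mg/m², and no section defines CB-839 dose intensity, a named part of the primary tolerability endpoint

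*SAP*

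**What the plan says.** **Nivolumab.** Protocol 11.1: "Nivolumab will be administered at a flat dose of 240 mg IV infusion over 60 min", on Days 1 and 15 of each 28-day cycle. SAP section 5 agrees: "240 mg every 2 weeks without adjustment for body weight". SAP 7.5.1 nevertheless lists "total dose received (mg for CB-839 and mg/m"² among the exposure summaries, with the per-area unit attached to nivolumab.

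**CB-839 dose intensity.** Protocol 6.1 defines the first primary endpoint as clinical tolerability of the combination, "including dose intensity of CB-839, adverse events, and laboratory data". Of the SAP sections that could carry this:

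- SAP 5.2.2 lists adverse events and "Changes in vital signs, physical findings, and clinical laboratory test results following study treatment administration".
- SAP 7.5.1 lists treatment duration, total dose and number of cycles for each drug by cohort, and adds: "Percent of patients and cycles with dose delays and reductions will be calculated".
- SAP 7.7 records changes to the Cohort 4 assessor, Cohort 6, protocol deviations and iRECIST. Dose intensity is not mentioned.

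Protocol 16.6 names the safety variables as adverse events, laboratory results, ECG, weight and vital signs. Dose intensity is absent there too.

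**The concern.** There are two separate problems in the same short section.

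First, the nivolumab unit does not match the dosing. A per-area total divides a fixed amount by each patient's size. The resulting spread would look like variation in exposure, and a reader comparing cohorts could take a difference in build for a difference in drug received.

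Second, a quantity named in a primary endpoint has no definition in either document. Relative dose intensity depends heavily on its denominator: starting or current dose, and whether held days count. If this is left open, it will be chosen after the dosing data are known, or the component will go unreported. CB-839 is the agent whose tolerability in combination is under study. Protocol 10.8.2 allows reductions and interruptions after Cycle 1, 10.8.2.2 lets the two drugs be held independently, and 10.9 has missed doses skipped. Delivered and planned dose can therefore differ appreciably.

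**Working it through.** The plan states no figure on this point, so there is nothing to reproduce. The check compares the texts, with arithmetic to show size.

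**1. Nivolumab unit.** Inputs: 240 mg per infusion and two infusions per cycle (Protocol 11.1). Body surface area (BSA) is an assumption, because the documents give no values.

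| Assumed BSA (m²) | 240 / BSA (mg/m²) | 480 / BSA per full cycle (mg/m²) |
|---|---|---|
| 1.6 | 150.0 | 300.0 |
| 1.9 | 126.3 | 252.6 |
| 2.2 | 109.1 | 218.2 |

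The highest value exceeds the lowest by 2.2/1.6 − 1 = 37.5% with no difference in dose. The unit can also hide a real difference: 8 infusions at 1.6 m² give 1,920/1.6 = 1,200 mg/m², and 11 infusions at 2.2 m² give 2,640/2.2 = 1,200 mg/m². Height is taken at screening and weight repeatedly, but the SAP gives no BSA formula and no rule for which weight to use. In mg, every patient has 240 per infusion and 480 per full cycle.

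**2. Planned CB-839 per cycle.** "CB-839 dosing will not be adjusted for body weight or surface area" (Protocol 11.1), and the planned number of doses is 56 per cycle ("43 of 56 total doses" is the evaluability threshold in Protocol 16.4.2).

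- 600 mg BID: 56 × 600 = 33,600 mg.
- 800 mg BID: 56 × 800 = 44,800 mg, or 1,600 mg/day.

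**3. Why total dose and duration summarised separately are not enough.** Take 89,600 mg in total (two full cycles at 800 mg BID). Relative dose intensity = total mg / (1,600 × days).

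| Days | mg/day | Relative dose intensity |
|---|---|---|
| 56 | 1,600.0 | 100% |
| 84 | 1,066.7 | 66.7% |
| 112 | 800.0 | 50% |

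The ratio must be formed for each patient before it is summarised. A cohort mean of total dose and a cohort mean of duration do not yield its distribution. The percentages with delays and reductions count occurrences; they do not measure how much planned drug was lost. A forgotten dose need not appear as either.

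**4. Why the denominator must be written down.** Two hypothetical patients starting at 800 mg BID:

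- *Reduction.* 28 days at 800 mg BID, then 28 days at 600 mg BID: 44,800 + 33,600 = 78,400 mg. Against the starting dose, 78,400/89,600 = 87.5%. Against the current dose at each time, 100%.
- *Hold that ends in discontinuation.* 56 days at full dose, then a 28-day hold, then stopped. Counted to last dose, 89,600/(1,600 × 56) = 100%. Counted to discontinuation, 89,600/(1,600 × 84) = 66.7%.

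**The case against.** The best reply is that SAP 7.5.1 already reports what a reader needs. It gives duration, total dose, cycles, and the percentage of patients and cycles with delays and reductions, separately for each drug. SAP 7.5.2 adds a table of treatment-emergent events leading to discontinuation or interruption. The exposure list is also worded as open-ended, so a ratio of its items is not excluded. This stands to a large extent. A reader might infer that the SAP ignores reduced dosing, or that this part of the endpoint goes wholly unexamined. The documents do not support that: the ingredients are planned, and what is missing is the defined patient-level statistic.

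A reader might also infer that the SAP alone dropped something the protocol had specified, or dropped it on purpose. Neither follows. Protocol 16.6 also omits dose intensity, so the mismatch begins inside the protocol, between 6.1 and 16.6. SAP 7.7 is silent on intent.

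On nivolumab, the reply is that this is a unit slip in one row and that the SAP's own design section makes the dosing clear. That is fair as to extent: nivolumab duration, cycles and delays are unaffected. It is still the stated rule, and a programmer following it would produce the distorted row.

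Finally, no decision rule uses either item. Escalation rests on dose-limiting toxicities and cohort decisions on responses. That is correct and limits the importance of the point.

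**Conclusion.** The point holds in two limited parts. The nivolumab total-dose unit in SAP 7.5.1 conflicts with flat dosing in both documents. CB-839 dose intensity is named in the primary tolerability endpoint but is neither defined nor planned in Protocol 16.6 or SAP 5.2.2 and 7.5.1, and it is not declared as dropped. The SAP's table of contents shows no other exposure section where it could sit.

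The 37.5% spread follows from the assumed BSA range of 1.6 to 2.2 m² and is an illustration, not an estimate for this trial. The dose-intensity examples use the documents' planned doses with hypothetical patients. The consequence is confined to tolerability reporting; ORR, sample size and error rates are untouched. It is worth correcting because one part is a wrong analysis rule and the other is a named primary endpoint component without a definition.

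**What to change.** 1. In SAP 7.5.1, report nivolumab total dose in mg and the number of infusions received.
2. In SAP 7.5.1, add CB-839 relative dose intensity = total mg taken / (protocol-planned daily mg at the patient's starting dose level × days from first dose to the treatment-discontinuation date or data cutoff). State that held and reduced days stay in the denominator, and that the discontinuation date is not replaced by the date of the last dose taken. Summarise by cohort and starting dose level.
3. List CB-839 relative dose intensity in SAP 5.2.2, so that the SAP matches Protocol 6.1.

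The cost is a short text edit and one derived variable, with no change to treatment or visits. The numerator is already needed for the planned total-dose summary. Capsule and tablet counts are recorded under Protocol 11.4 and 11.5, but in a drug accountability log copied to the sponsor at study end. The documents do not say that these counts reach the analysis database, so the data source for mg taken should be confirmed and named.

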### **7.5.2 Adverse Events**

Verbatim description of adverse events will be coded to System Organ Class (SOC) and Preferred Term (PT) using the Medical Dictionary for Regulatory Activities (MedDRA) and graded by the investigator according to NCI CTCAE v4.03. Treatment-emergent AEs (TEAEs) are defined as AEs started or worsened on or after first dose and will be tabulated. The number and proportion of patients reporting a given TEAE will be tabulated according to the worst severity grade reported. Separate tables will be constructed for a) all reported TEAE's, b) serious TEAEs (treatment-emergent SAEs), c) severe TEAEs (Grade  $\geq 3$ ), and d) TEAE's leading to permanent discontinuation or interruption of study treatments. The above tables will also be presented for TEAEs judged to be related to either study treatment.

Multiple occurrences of the same event will be counted once at the maximum grade. In order to accurately summarize the true TEAE rate, all TEAE summaries will not count grade 5 events for patients who died due to progressive disease.

All listings of adverse events will include both TEAEs and non-TEAEs.

Deaths reported during the study treatment period and the follow-up period after treatment completion/discontinuation will be listed and summarized by cause.

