### 10.8.2.2 Resumption of Study Treatment

For both CB-839 and nivolumab, treatment may be delayed for up to 4 weeks from the last dose before restarting. CB-839 and nivolumab may be held and restarted independent of each other. Treatment delays longer than 4 weeks are allowed only in cases where a prolonged steroid taper is required to manage drug-related AEs or, in some cases, if the delay was due to a non-drug related cause. Prior to re-initiating treatment in a patient with a dosing interruption lasting > 4 weeks, the Medical Monitor must be consulted. Treatment compliance will be monitored by drug accountability as well as the patient's medical record and eCRF.

Upon withholding study drug(s) for adverse events, the study drug(s) may be restarted when the AE has returned to  $\leq$  Grade 1. For patients that require a steroid taper, nivolumab should not be restarted until the steroid taper is complete. In cases in which a particular toxicity is clearly related to only one of the two study drugs, the study drug that is not involved in causing the AE may be continued or restarted prior to AE resolution to  $\leq$  Grade 1 or baseline. If CB-839 is restarted after permanent discontinuation of nivolumab, CB-839 should also be permanently discontinued for a  $\geq$  Grade 3 recurrence of the AE that resulted in nivolumab discontinuation.

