## 16.6 Safety Analysis

Safety variables to be analyzed by tumor type are AEs, laboratory test results (hematology, coagulation, serum chemistry, and urinalysis), ECG, weight, and vital signs.

Adverse event terms recorded on the eCRFs will be mapped to preferred terms using the most recent version of the Medical Dictionary for Drug Regulatory Activities (MedDRA®). All AEs will be summarized according to the system organ class and preferred term within the organ class. Adverse events will be tallied for overall frequency (number and percentage of patients), worst reported severity, and relationship to study drug for each preferred term per patient. Serious adverse events will be similarly summarized. Listings of deaths, SAEs, and AEs leading to early termination of study treatment or premature withdrawal from study will also be provided.

Laboratory variables will be examined using mean change in value from baseline to scheduled time points. The baseline value of a variable is defined as the last value obtained on or before the date and time of the first dose of CB-839 or nivolumab.

ECG, weight, and vital signs will also be summarized by changes from baseline to scheduled time points using descriptive statistics.

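### SAP table (d) pools adverse events that end treatment with those that only interrupt it, over both drugs, so it cannot show AE-related discontinuation of CB-839 or of nivolumab

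*SAP*

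**What the plan says.** SAP 7.5.2 sets out the adverse event tables: "Separate tables will be constructed for a) all reported TEAE's", then serious events, then Grade 3 or higher events, and last, as item (d), events "leading to permanent discontinuation or interruption of study treatments". The same set is repeated for events judged related to either study treatment. Patients are tabulated by worst grade, and repeated occurrences of the same event count once at the maximum grade. On listings, the section says only: "All listings of adverse events will include both TEAEs and non-TEAEs".

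Protocol 16.6 treats events that end treatment as an output of their own: "Listings of deaths, SAEs, and AEs leading to early termination of study treatment or premature withdrawal from study will also be provided". Interruptions are not part of that listing.

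Protocol 6.1 makes safety and tolerability of the combination a primary objective, with this endpoint: "Evaluation of clinical tolerability of CB-839 in combination with nivolumab, including dose intensity of CB-839, adverse events, and laboratory data". On dosing, protocol 10.8.2.2 states that "CB-839 and nivolumab may be held and restarted independent of each other".

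**The concern.** A hold that is later lifted and a permanent stop are different tolerability outcomes. Protocol 17.1 itself names dose modification, interruption and permanent discontinuation as distinct consequences of an abnormal result. Item (d) merges two of these and merges the two drugs as well.

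The question for this trial is how well CB-839 is tolerated when added to nivolumab. A reader of the safety report will want to know how often an adverse event forced patients off CB-839, and how often off nivolumab. Protocol 6.3.1.4 and 6.3.2 allow the recommended dose to be amended in the light of expansion-phase safety data, so these are practical questions. On the present wording, the one planned table that links adverse events to treatment changes does not answer either of them.

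**Working it through.** No figure in either document can be reproduced here, because neither states a discontinuation or interruption rate. The check compares the planned outputs.

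**1. What item (d) identifies.** Let D be the patients with an event leading to permanent discontinuation of either drug, and I those with an event leading to interruption. Item (d) counts M = |D ∪ I| = |D| + |I| − |D ∩ I|. Given only M, |D| can be any value from 0 to M. The same bound applies to discontinuation of CB-839 alone and of nivolumab alone, since each is a subset of D.

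**2. Whether the two drugs diverge within one event.** Protocol Table 10.8-1 has 14 rows that permanently discontinue nivolumab: one in each of the ten named categories (colitis, pneumonitis, hepatitis, hypophysitis, adrenal insufficiency, diabetes, nephritis, skin, infusion reaction, encephalitis) and four under other irAEs. For CB-839, those rows say:

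- hold, with re-challenge as monotherapy to be considered: 11 rows (nine named categories and two under other irAEs);
- consider re-challenge or continuation as monotherapy: 1 row (prolonged steroid requirement);
- no CB-839 action stated: 1 row (infusion reaction);
- permanent discontinuation: 1 row (persistent Grade 2 or 3 reactions).

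11 + 1 + 1 + 1 = 14. So in 11 of the 14 rows, one event is a discontinuation of nivolumab and an interruption of CB-839. Item (d) records it once, without saying which drug had which outcome.

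**3. Whether grade recovers the outcome.** It does so only in part. In Table 10.8-1, Grade 3 colitis holds both drugs, while Grade 3 pneumonitis permanently stops nivolumab. For other Grade 3 irAEs, a first occurrence is a hold, and a recurrence of the same event permanently stops nivolumab. Because SAP 7.5.2 counts repeats of one event once at maximum grade, a patient with the first occurrence only and a patient with the recurrence give the same entry.

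**4. What the other outputs supply.**

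- SAP 7.2 summarises the reason for discontinuation from the study. Under protocol 10.6, patients who stop treatment are still followed for survival, and by imaging if they stopped for a reason other than progression. Leaving the study and stopping a drug are therefore different events, and 7.2 is not per drug.
- SAP 7.5.1 summarises exposure for CB-839 and nivolumab separately, including delays and reductions. These are from any cause, and permanent stops are not among the items named.
- The protocol 16.6 listing covers events ending treatment, but it is combined with withdrawal from study and gives no rate. The SAP does not name it, and SAP 7.7 records no decision to drop it.

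Taken together, these outputs do not give the number of patients who permanently stopped a given drug because of an adverse event.

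**The case against.** The strongest case on the other side is that nothing planned is contradicted or lost. Several parts of it stand.

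- A reader might infer that the SAP replaces a discontinuation rate promised in the protocol. It does not. Protocol 16.6 promises a listing, not a rate, and the SAP table is an addition to it.
- A reader might infer that a discontinuation rate is part of the primary tolerability endpoint. Protocol 6.1 names dose intensity, adverse events and laboratory data; SAP 5.2.2 names no discontinuation rate either. No decision rule uses one.
- A reader might infer that the SAP ignores dose reductions and never separates the drugs. SAP 7.5.1 does both, though not by cause.
- A reader might infer that the pooled figure must far exceed the discontinuation rate. Table 10.8-1 sets actions by severity and gives no frequencies, so any ratio would rest on invented counts.

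It can also be said that item (d) names a table topic and does not forbid separate rows. That is fair: a table shell showing the outcomes apart would settle the point, but the SAP text does not require one. A hand count from the protocol listing is possible too, but it is not a planned summary, and the listing as described is not per drug.

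**Conclusion.** The point holds as a reporting gap. As written, item (d) does not identify AE-related discontinuation of either drug, and the other planned outputs fill the gap only in part. It is not a conflict between protocol and SAP over a rate, and not an error in a primary analysis.

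Its size cannot be stated as a percentage from these documents; the only bound is that the discontinuation count lies between zero and the table total. The conclusion assumes that item (d) is produced as worded, without a split added in the table layouts. It is best classed as a cheap improvement that makes the tolerability objective readable.

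**What to change.** In SAP 7.5.2, split item (d) into (i) events leading to permanent discontinuation and (ii) events leading to interruption. Add (iii) events leading to CB-839 dose reduction, if that attribution was collected. Within each, give rows or columns for CB-839, nivolumab and both drugs, and repeat for related events. State in the same section that the protocol 16.6 listing of deaths, serious events and events ending treatment or participation will be produced.

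The cost is a sentence or two of SAP text and some extra table rows; columns within existing tables keep the number of displays down. The change depends on action taken having been recorded separately for each drug on the adverse event or dosing pages. If it was not, the split by outcome should still be made, with the missing split by drug stated as a limitation. No change to dosing or study conduct is involved.

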- Additionally, important medical events that may not result in death, be life-threatening, or require hospitalization may be considered SAEs when, based on appropriate medical judgment, they may jeopardize the patient and may require medical or surgical intervention to prevent one of the outcomes listed in this definition. Examples of such events include allergic bronchospasm requiring intensive treatment in an emergency room or at home, blood dyscrasias or convulsions that do not result in hospitalization, or development of drug dependency or drug abuse.

**Clear progression of neoplasia should not be reported as an AE or SAE** (unless the investigator considers the progression of underlying neoplasia to be atypical in its nature, presentation or severity from the normal course of the disease in a particular patient). Findings that are clearly consistent with the expected progression of the underlying cancer should not be

reported as an adverse event, and hospitalizations due to the progression of cancer do not necessarily qualify for an SAE. All deaths including those related to progression of disease and sudden and unexplained death should be reported as an SAE. If there is any uncertainty about a finding being due solely to progression of neoplasia, the finding should be reported as an AE or SAE as appropriate.

**Life-threatening**, in the context of an SAE, refers to *immediate risk of death* as the event occurred per the reporter. A life-threatening experience does not include an experience, had it occurred in a more severe form, which might have caused death, but as it actually occurred, did not create an immediate risk of death. For example, hepatitis that resolved without evidence of hepatic failure would not be considered life-threatening, even though hepatitis of a more severe nature can be fatal. Similarly, an allergic reaction resulting in angioedema of the face would not be life-threatening, even though angioedema of the larynx, allergic bronchospasm, or anaphylaxis can be fatal.

**Hospitalization** is official admission to a hospital. Hospitalization or prolongation of a hospitalization constitutes criteria for an AE to be serious; however, it is not in itself considered a serious adverse event (SAE). In the absence of an AE, a hospitalization or prolongation of a hospitalization should not be reported as an SAE. This is the case in the following situations:

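### SAP 7.5.2 drops Grade 5 events from all TEAE tables by the patient's cause of death rather than by the event, so a fatal event that is not progression can go uncounted as a TEAE

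*SAP*

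**What the plan says.** SAP 7.5.2 introduces the rule with its purpose, "In order to accurately summarize the true TEAE rate", and then states that "all TEAE summaries will not count grade 5 events for patients who died due to progressive disease". The same section defines the tables affected: "Separate tables will be constructed for a) all reported TEAE's, b) serious TEAEs (treatment-emergent SAEs), c) severe TEAEs" of Grade 3 or higher, and a fourth set for events leading to permanent discontinuation or interruption. It then adds that "The above tables will also be presented for TEAEs judged to be related to either study treatment".

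Two other sentences in that section limit the effect. On listings: "All listings of adverse events will include both TEAEs and non-TEAEs". On deaths: "Deaths reported during the study treatment period and the follow-up period after treatment completion/discontinuation will be listed and summarized by cause".

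Protocol 17.1 explains why a rule of this kind is wanted. It says that "Clear progression of neoplasia should not be reported as an AE or SAE", with an exception for atypical progression, but also that "All deaths including those related to progression of disease and sudden and unexplained death should be reported as an SAE". Where it is uncertain whether a finding is due solely to progression, 17.1 asks for it to be reported.

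Protocol 16.6 plans summaries of AEs by system organ class and preferred term, with severity and relationship, and has no Grade 5 exclusion. SAP 7.7, which lists changes to the planned analyses, does not mention one.

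**The concern.** The aim is to keep deaths from cancer out of the adverse event rates. The rule as worded does something wider: once a patient's death is attributed to progression, any Grade 5 event in that patient is not counted, whatever the event was.

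Safety and tolerability of the combination is a primary objective (protocol 6.1), and protocol 10.8.1.3 describes that tolerability as unknown. The cohorts are single-arm and open-label, so there is no control group against which a misattributed fatal event would stand out. Protocol 10.8.1.2 names pneumonitis and hepatitis among the immune-related events of nivolumab. In patients with advanced cancer, including lung cancer, such an event and progression may coexist near death.

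The rule can only lower the Grade 5 counts or leave them unchanged. Elsewhere the SAP leans the other way: section 7.6 treats an AE with missing relationship as related, and one with an unresolved start date as treatment-emergent.

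**Working it through.** The plan gives no figure on this point, so there is none to reproduce. The check is mainly a reading of the text.

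**Step 1: the trigger.** The only condition in the rule is that the patient died of progressive disease. Nothing is said about the event's term, its cause, or its relationship to CB-839 or nivolumab.

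**Step 2: the reach.** The rule covers all TEAE summaries: overall, serious, Grade 3 or higher, and discontinuation or interruption. Each is repeated for related events. There is no exception for the related versions.

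**Step 3: the rule applied to possible cases.**

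| Grade 5 event | Death attributed to | Counted in TEAE tables? | Fits the rule's aim? |
|---|---|---|---|
| Reported as disease progression | Progression | No | Yes |
| Organ term, due solely to progression | Progression | No | Yes |
| Organ term, not progression, possibly judged related | Progression | No | No |
| Organ term, not progression | Toxicity or other cause | Yes | Yes |

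Only the third row is a problem. It arises when the attributed cause of death and the recorded event disagree, because causes are mixed or the attribution is wrong.

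**Step 4: where the third-row event remains visible.** It is in the AE listings. The death is in the death listing and in the summary of deaths by cause, but under progression. No planned summary table shows the event as a fatal toxicity.

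**Step 5: what the SAP leaves open.** It does not say who assigns the cause of death, how mixed causes are handled, or whether a patient with an excluded Grade 5 event drops out of the row for that term or is shown at the next-worst grade.

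**Step 6: SAP against protocol.** Protocol 16.6 has no exclusion, SAP 7.5.2 has one, and SAP 7.7 does not list it. This is an undeclared change to a planned analysis.

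**Step 7: scale, as an illustration only.** Assume that exactly one third-row event is removed in a cohort. SAP 7.1.3 analyses safety by cohort, so the denominators are the smallest and largest planned totals among Cohorts 1 to 5 in SAP Table 1: 24 (Cohort 3) and 75 (Cohort 4). The SAP plans no intervals for AE rates; exact 95% Clopper-Pearson limits are used here only to show precision. For x events in n patients, the lower limit is the 0.025 quantile of Beta(x, n − x + 1) and the upper limit is the 0.975 quantile of Beta(x + 1, n − x). With x = 0 the lower limit is 0 and the upper is 1 − 0.025^(1/n).

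- n = 24, counted: 1/24 = 4.2%, 95% CI 0.1% to 21.1%.
- n = 24, removed: 0/24 = 0%, upper limit 1 − 0.025^(1/24) = 14.2%.
- n = 75, counted: 1/75 = 1.3%, 95% CI 0.03% to 7.2%.
- n = 75, removed: 0/75 = 0%, upper limit 1 − 0.025^(1/75) = 4.8%.

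The intervals overlap heavily. What changes is the entry in the table: a cohort with one reported fatal event that was not progression would show none.

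**The case against.** The best defence is that the rule answers a real problem. Protocol 17.1 keeps clear progression out of the AE data but sends every death in as an SAE, so without some exclusion deaths from cancer would inflate the Grade 5 counts. The affected case is also narrow. A death attributed to toxicity is outside the rule and stays in every table. Protocol 17.1 tells sites to report uncertain findings and to presume relatedness unless stated criteria are met, the sponsor evaluates every SAE (protocol 17.3), and a sponsor team reviews aggregate safety data (SAP 6.1). All of this stands. It limits how often the problem could arise, but it does not change what the tables would show when it does.

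A reader might infer that fatal toxicities vanish from the safety reporting. The documents do not support that: the listings keep the event, and the death is both listed and summarized. A reader might also take cause of death to be the investigator's judgement. The SAP gives AE grading to the investigator, but neither document says who assigns the cause of death for this summary.

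It is also tempting to size the effect over full enrolment of Cohorts 1 to 5, 52 + 56 + 24 + 75 + 56 = 263. That total pools cohorts that the SAP analyses separately. It adds up response-evaluable targets rather than treated patients, and it assumes that every cohort completes Stage 2.

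Finally, the obvious remedy of excluding only events whose preferred term is disease progression would not work alone. Because protocol 17.1 bars clear progression as an AE and 17.2 asks for a specific diagnosis where feasible, a death from cancer may be entered under an organ term, and that filter would count it as a fatal TEAE.

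**Conclusion.** The point holds as a defect in how the exclusion is defined. As written, SAP 7.5.2 leaves a Grade 5 event that is not progression, including one judged related, out of every TEAE table whenever the death is attributed to progressive disease. The departure from protocol 16.6 is not declared.

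The frequency cannot be derived from the documents, which do not say how often the attributed cause and the recorded event would differ. The per-cohort figures rest on the assumption of one removed event and on planned cohort sizes. They show that a single event decides between a zero and a non-zero fatal count in a cohort; they do not estimate the number lost. Because safety is a primary objective and the correction is cheap, the rule should be reworded before the tables are produced.

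**What to change.** Reword the exclusion in SAP 7.5.2 so that it works per event:

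- Exclude a Grade 5 event from the TEAE summaries only if it is reported as disease progression or is documented as due solely to progression.
- Never exclude an event judged related to either study treatment.
- State who assigns the cause of death, how mixed causes are handled, and whether an excluded event is dropped or shown at the next-worst grade.
- Add one table by cohort of all Grade 5 TEAEs without the exclusion, by preferred term, attributed cause of death and relationship.
- Record the departure from protocol 16.6 in SAP 7.7.

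The cost is a few lines of SAP text, one extra table, and a documented judgement for each Grade 5 event that is to be excluded. Grade 5 counts may be slightly higher than under the present rule.
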